#### 14.3 Data management

All data management procedures will be detailed in a Data Management Plan (DMP).

The DMP will describe the Clinical Data Management System (CDMS) that will be used to collect data. The study data will be collected on an electronic data capture (EDC) set up by the CRO. Computerized edit checks and review processes will be performed on an ongoing basis until all data clarifications are resolved. The data will be exported from MySQL database to be stored in appropriate format. After all data clarifications are resolved, coding is approved, and subject's evaluability is determined, the database will be locked.

## 14.4 Quality assurance / audit / inspection

The clinical trial is conducted under the sponsorship of DDS Ltd in compliance with the applicable international and local regulatory requirements as well as applicable ICH guidelines and in accordance with the SOPs for clinical trial conduct and monitoring from the assigned Contract Research Organization (CRO), Adhoc Clinical.

Audits of the clinical trial center may be conducted by the Sponsor/CRO representatives, and inspection may be performed by Regulatory Authority inspectorates or IECs before, during, or after the clinical trial.

The Investigator will allow and assist the CRO/Sponsor's representatives, IECs and any regulatory agency to have direct access to all requested clinical trial-related records.

For the audits performed by, or on behalf of, sponsors auditors, audit certificate(s) will be provided by Quality Assurance.

## 14.5 Changes in clinical trial conduct / amendments

#### 14.5.1 Clinical trial conduct

With the exception of eliminating an immediate hazard to a subject, the Investigator should not deviate from the clinical trial protocol or implement any changes without written approval from the Sponsor and prior review and documented approval/favourable opinion from the IEC of a protocol amendment.

Changes that involve only logistical or administrative changes to the clinical trial protocol are authorized. The Investigator should document and explain any deviation from the clinical trial protocol.

### 14.5.2 Amendments

The Sponsor may modify the clinical trial protocol at any time for ethical, medical, or scientific reasons.

Clinical Trial Protocol MC2-01-C4

Final Approved Version 20/08/2018

Protocol change to be submitted (Changes as per Substantial amendment in EU):

No amendment can be implemented at clinical trial center, unless to eliminate an immediate hazard to the subjects, without having obtained a favorable opinion from the appropriate Regulatory Authority and/or the IEC in compliance with applicable regulation(s).

Protocol change not to be submitted (Non-substantial amendment for EU):

An amendment will not be issued for modification(s) due to change in logistical or administrative aspects of the clinical trial (e.g., change in contact details for the Sponsor or Sponsor representative) or for non-substantial amendments for the clinical trial center within the European Union. In such cases, these changes will be documented and communicated to clinical trial center in the most appropriate way depending on the nature of the change.

## **15 ETHICS AND GENERAL CLINICAL TRIAL CONDUCT CONSIDERATIONS**

## 15.1 Independent Ethics Committee (IEC)

This clinical trial protocol and all amendments will be reviewed and approved by the appropriate IECs.

## 15.2 Ethical conduct of the clinical trial

This clinical trial will be conducted in accordance with the protocol, the HELSINKI declaration (1964) and subsequent amendments, and the ICH GCP, and in compliance with applicable regulatory requirements.

## 15.3 Subject information and consent

All subjects who participate in this clinical trial are required to be fully informed about the clinical trial in accordance with GCPs guidelines and in accordance with local requirements.

All subjects recruited for this clinical trial will be registered in the National File of Persons Participating in Research involving the Human Person.

The ICF, approved by an IEC, will be fully explained to the subject.

Prior to enrolment into the clinical trial, the subject will sign and date the consent form(s). The Investigator is responsible for maintaining each subject's consent form(s) in the Investigator's site file and providing each subject, with a copy of the signed and dated consent form(s).

## **15.4** Protection of Personal Data

CPCAD is registered by the French Commission Nationale de l'Informatique et des Libertés (CNIL) as complying with the MR-001 Reference Methodology for processing clinical trial data (Declaration

CONFIDENTIAL

Clinical Trial Protocol MC2-01-C4

Final Approved Version 20/08/2018

number 1246487). CPCAD also complies with the local French GDPR (General Data Protection Regulation) law that entered into force on 25 May 2018. The GDPR allows the subject to exercise his/her rights of rectification, opposition, deletion, portability and limitation of the procession of his/her personal data. To assert this right, the volunteer can contact the Investigator.

## 15.5 Regulatory Authority

The written authorization of the clinical trial by the regulatory authorities (ANSM) will be required prior to the trial implementation.

## **15.6 Contractual requirements**

A contractual agreement will be signed between the CRO/Sponsor and each Investigator/Institution. This document will contain supplementary information, including financial terms, confidentiality, the clinical trial schedule, third party responsibility, and publication rights.

## 15.7 Data collection and archiving

## 15.7.1 Data collection

The Investigator must maintain all required records for all subjects. Data for this clinical trial will be recorded in the subject's source documents and on the CRFs provided by the Sponsor. All data should be recorded on the CRFs completely and promptly, and legibly using black ink. A complete set of copies will remain at the clinical trial center with the related data clarification forms.

## 15.7.2 Source documentation

The Investigator must keep accurate separate records (other than the CRFs) of all subject visits, being sure to include all pertinent clinical trial-related information. A statement should be made indicating that the subjects have been included in this clinical trial and have provided signed written Informed Consent. All AEs must be thoroughly documented.

Results of any diagnostic tests conducted during the clinical trial should also be included in the source documentation.

## 15.7.3 Archives

All pertinent data, correspondence, and reports, the original or amended clinical trial protocol, and all other material relating to the clinical trial will be maintained securely in Sponsor/CRO/Investigator/ Institution archives for the legally required duration for archiving (15 years after the end of the research or after its premature termination).

The Investigator/Institution should maintain the essential clinical trial documents as specified in Section 8 of ICH GCP, and according to the applicable regulatory requirements.

#### CONFIDENTIAL

Clinical Trial Protocol MC2-01-C4

Final Approved Version 20/08/2018

The Investigator/Institution should take measures to prevent accidental or premature destruction of these documents.

If the Principal Investigator retires, relocates, or withdraws from the responsibility of keeping the clinical trial records for any other reasons, custody must be transferred to a person who will accept the responsibility. The Sponsor/CRO must be notified in writing of the name and address of the new custodian.

## 15.8 Insurance

A certificate attesting Third Party coverage of CRO/Sponsor will be provided upon request.

## 15.9 Investigator and Administrative Structure

Not applicable

CONFIDENTIAL

Clinical Trial Protocol MC2-01-C4

## **17 APPENDICES**

Appendix 1: Summary of Product Characteristics (SmPC)/ Product Monographs for Investigational Products – Clobex® lotion

Appendix 2: Summary of Product Characteristics (SmPC)/ Product Monographs for Investigational Products – Betamethasone Dipropionate (Augmented)

Appendix 3: Summary of Product Characteristics (SmPC)/ Product Monographs for Investigational Products – Triamcinolone Acetonide cream

Appendix 4: Summary of Product Characteristics (SmPC)/ Product Monographs for Investigational Products – Locoid® cream

Appendix 5: Summary of Product Characteristics (SmPC)/ Product Monographs for Investigational Products – DesOwen® cream

# **VERSION HISTORY**

Version	Date of Issue	Reason for change	
Version #1.0	30-Oct-2018	[name] issued the first version.	
Version #2.0	05-Dec-2018	[name] implemented the changes required by [name] and [name] and issued the second version.	

#### 1 LIST OF ABBREVIATIONS AND DEFINITIONS OF TERMS

ADR	Adverse Drug Reaction
AE	Adverse Event
BDP	Betamethasone dipropionate
CPCAD	Centre de Pharmacologie Clinique Appliquée à la Dermatologie = name of
	the trial site
FAS	Full Analysis Set
IMP	Investigational Medicinal Product
IP	Investigational Product
IRB	Institutional Review Board
LOCF	Last Observation Carried Forward
Max	Maximum
MedDRA	Medical Dictionary for Regulatory Activities
Min	Minimum
Ν	Number of subjects
PP	Per Protocol
РТ	Preferred Term
SAE	Serious Adverse Event
SD	Standard Deviation
SOC	System Organ Class

#### **2** STUDY OBJECTIVES

#### 2.1 Primary study objective

The objective of this trial is to compare the vasoconstriction potential (skin blanching effect) of MC2-01 cream with Clobex® 0.05% (clobetasol propionate) lotion, Betamethasone Dipropionate (Augmented) cream, Triamcinolone Acetonide 0.1% (triamcinolone acetonide) cream, Locoid® 0.1% (hydrocortisone butyrate) cream, Desowen® 0.05% (desonide) cream and MC2-01 vehicle using the human skin blanching test (McKenzie-Stoughton's test).

#### 2.2 Secondary study objectives

The objective of this trial is to assess the local tolerability of MC2-01 cream and the matching vehicle.

#### **3** STUDY DESIGN

#### 3.1 Study type

This is a single center, investigator blinded, active - and vehicle-controlled, single application, intra-individual comparisons on mini-test sites (n=7), involving 36 healthy subjects meeting specific inclusion/exclusion criteria.

Eligible subjects will receive a single application of each of the following:

- **MC2-01 cream** containing calcipotriol and betamethasone dipropionate, w/w 0.005% / 0.064%.
- MC2-01 cream vehicle
- **Clobex® lotion** containing clobetasol propionate 0.05%
- Betamethasone Dipropionate (Augmented) cream
- **Triamcinolone Acetonide** containing triamcinolone acetonide 0.1%
- **Locoid® cream** containing hydrocortisone-17-butyrate 0.1%
- **Desowen® cream** containing desonide 0.05%

The trial will employ an unoccluded McKenzie-Stoughton trial design based on topical application of a corticosteroid-containing formulation for a period of 16 hours in healthy human volunteers followed by visual estimation of the degree of blanching on a multiple unit scale (0 to 4) by two independent trained observers 2 hours after the end of the application period. The trial will be conducted with three successive individual phases:

- **Screening phase** with a screening blanching test.
- Test phase
- **Follow-up phase**. For subjects with a local tolerability scores >0 at Day 2 or if a non-serious adverse event classified as reasonably or possibly related to the investigational products or a Serious Adverse Event (SAE) is ongoing once a subject has completed the test phase (Day 2), a follow-up visit/contact will take place up to 14 ( $\pm$ 2) days after the end of test phase (Day 2). SAEs will be monitored until the

Investigator and Sponsor agree that the event is satisfactorily resolved; telephone contact or visit according to the investigator's discretion.

#### 3.2 Study duration

Clinical trial participation for each subject is of 2 days plus the screening phase and a possible follow-up phase.

#### 3.3 Study schedule

Trial Phases:	Screening	Test		Follow-up 
Trial Days :	Day-15 to Day- 1	Day1	Day2	Day15 (±2days)
Informed Consent Form	V			
Demographics/Medical history				
Previous treatments/procedures	Ŋ			
Inclusion/exclusion criteria	V	V		
Selection of test sites		Ø		
Physical exam, vital signs	V			
Urine pregnancy test 	Ø	Ø		
Screening test for blanching response	Ø			
Randomization		Ø		
Local tolerance 			V	Ø
Application of IMPs		Ø		
Product excess removal 			V	
Measurement of skin blanching by 2 trained evaluators 			V	
Concomitant treatments	$\mathbf{\nabla}$	V	V	Ø
Adverse events	$\mathbf{\nabla}$	V	V	Ø
End of treatment			V	
End of study				Ø

1: For female subject of childbearing potential. Result must be negative to continue the trial.

2: For subjects with a local tolerability scores >0 at Day 2 or if a non-serious adverse event classified as reasonably or possibly related to the investigational products or an SAE is ongoing once a subject has completed the test phase (Day 2), a follow-up visit/contact (telephone contact or visit according to the investigator's discretion) will take place up to 14 ( $\pm$ 2) days after the end of test phase (Day 2). AEs and SAEs assessed as reasonably or possibly related to the trial medication must be followed until resolved or until the medical condition of the subject is stable.

3: 16 hours +/- 30 min after IMP application

4: 2 hours +/- 30 min after IMP removal

Statistical Analysis Plan MC2-01-C4 / CPCAD CPC-3530 Version 2.0 dated 05-Dec-2018 Page 8/16

#### **3.4** Population characteristics

Approximately 60 subjects will be pretested in order to have 36 subjects randomized and at least 30 subjects completed.

#### 3.5 Study treatments

#### Table 2 – Study treatments

	Investigational product 1	Investigational product 2	Reference product 1	Reference product 2	Reference product 3	Reference product 4	Reference product 5	
Trade Name or Equivalent	MC2-01	MC2-01 vehicle	Clobex® (Galderma Labs LP)	Betamethasone Dipropionate (Augmented) (Taro Pharmaceuticals)	Triamcinolone Acetonide (Ascend Laboratories LLC)	Locoid® (Precision Dermatology)	Desowen® (Galderma Labs LP)	
Name of Drug Substance	Calcipotriol + Betamethasone dipropionate	NA	Clobetasol propionate	Betamethasone dipropionate	Triamcinolone acetonide	Hydrocortisone butyrate	Desonide	
Pharmaceutical Form	cream	cream	lotion	cream	cream	cream	cream	
Concentration	0.005% + 0.064%	NA	0.05%	0.064% w/w (equivalent to 0.05% betamethasone)	0.1%	0.1%	0.05%	
Package	60 g aluminium tubes	60 g aluminium tubes	Bottle 59ml	15 g aluminium tubes	30 g tube	30 g aluminium tube	60 g tube	
Storage conditions	Store between 2-8°C between treatment days – May be store at room temperature below 25°C at the day of treatment application		Store below 30°C	Do not store above 25°C	Store at 20- 25°C	Do not store above 25°C. Do not refrigerate or freeze	Store between 2° and 30°C	
Dosage (per site)	20 µL	20 µL	20 µL	20 µL	20 µL	20 µL	20 µL	
Route	Topical (Cutaneous to the skin)							
Dose Regimen	A single application of each IMP							
Duration of administration	Contact duration of 16 hours (+/- 30 min)							
Location of Treated Area	Area of 2.2 cm diameter							

#### **4 STUDY EVALUATION**

#### 4.1 Visual assessment of skin blanching

Visual assessment of blanching will be made independently by two trained readers on Day 2 (2 hours after removal of products, following 16 hours application time) according to the following scale:

Table 3 -	Skin	blanching	visual	scale
Iunice	omi	Signeting	1 Duu	beare

	in standing visual scale
Score*	Description
0	No change in skin color
1	Slight (barely visible) blanching
2	Obvious blanching
3	Intense blanching
4	Blanching judged to be maximal

\*Intermediate scores (half units) may be used when needed (e.g. 0.5 for a doubtful blanching).

Two visual score values (one per trained evaluator) will be recorded for each test site.

#### 4.2 Assessment of local tolerability

At Day 2, the (sub)investigator will assess each test site for local tolerability according to the scale in Table 4.

	Table 4 - Local tolerability scale						
Score*	Description						
0	No reaction						
0.5	Only slight erythema						
1	Only erythema						
2	Erythema with papules or oedema						
3	Erythema, oedema with papules, oedema with vesicle						
4	Blisters						
IR	Irritant reaction including: miliaria (sweat rash), follicular pustules, burn-like reactions, dry scales						

 Table 4 - Local tolerability scale

Subjects with a local tolerability score >0 will be re-assessed at a follow-up visit.

Cutaneous reactions scored as local tolerability will be reported as local Adverse Events (AEs).

### 4.3 Safety assessment

A safety assessment will be conducted for all subjects at the screening visit (from the Informed Consent signature) and every subsequent visit. The safety parameters are AEs, to be recorded as specified in the protocol, global cutaneous tolerance assessments, physical examination and vital signs assessments (Screening visit only).

AEs will be reported individually on an ongoing basis.

All clinical medical events, whether observed by the Investigator or reported by the Subject will be considered as adverse events and recorded on the appropriate Adverse Event form. Assessment of severity and causality will be based on specific definitions.

#### **5** STATISTICAL METHODS

#### 5.1 Trial Population

#### 5.1.1 Definition

A detailed counting of subjects included or excluded from analysis will be performed prior to any data review and analysis. All protocol deviations will be reported.

All randomized subjects who receive any trial medication and who contribute any efficacy data in the trial will comprise the **full analysis set** (FAS) and will be analyzed for efficacy.

A **per protocol analysis set** (PP) will be defined by exclusion of subjects from the FAS, who do not fulfil all of the inclusion criteria or who meet any of the exclusion criteria. Further subjects and/or subject data may be excluded from the per protocol analysis when agreed upon on the basis of the actual data obtained as evaluated before breaking the randomization code.

[figure not shown]
All subjects who receive any treatment with trial medication and for whom the presence or confirmed absence of AEs is available will be included in the **safety analysis set** and analyzed for safety.

Statistical Analysis Plan MC2-01-C4 / CPCAD CPC-3530 Version 2.0 dated 05-Dec-2018 Page 11/16

The following chart will be completed to describe the different populations:

#### **Figure 1: Disposition of subjects**

A data blind review will be performed after the database lock and before breaking the randomization code. A listing of all protocol deviations will be provided, including the type (major/minor) and their consequences in terms of analysis, according to the decisions made by the reviewers.

A major protocol deviation is any event likely to biase significantly the interpretation of the efficacy results and especially the primary ones. Then, this type of deviation will lead to subject exclusion from the PP population. All other protocol deviations will be considered as minor.

A priori the following deviations will be considered as major:

- Deviations in inclusion and non-inclusion criteria at screening,
- Exclusion criteria during the study (pregnancy, health problems, protocol deviation / violation, consent withdrawal, intake of any product or treatment able to interfere with study results, onset of an intolerance to the study treatments),
- Evaluation of primary criterion non-available.

Other elements will be detailed to detect possible deviations:

- Consistency of the randomization scheme,
- Premature withdrawals from study,
- Medical and surgical history,
- Previous and concomitant treatments,
- Adverse events,
- Deviations in dates of visits.

Number and percentage of subjects having at least one minor protocol deviation will be presented by type and deviation class. Major deviations will be listed.

#### **5.1.2** Baseline characteristics

Summary statistics of subject characteristics (age, sex, skin type, height, weight and BMI) and of baseline characteristics (hormonal status, concurrent diagnoses and concomitant medication at baseline as well as screening test for skin blanching) will be tabulated.

The results will be presented as follows:

		Full Analysis Set (N=XX)
Quantitative	Ν	
variable	Mean±SD	
	Median	
	(Min,Max)	
Qualitative	Ν	
variable	Modality 1	N (%)
	Modality 2	N (%)
	Modality n	N (%)

## 5.2 . Analysis of pharmacodynamic effect (blanching)

#### 5.2.1 Primary pharmacodynamic criterion

The analysed variable will be the mean between the two readers at each evaluation time.

The results will be expressed by the mean values obtained at each assessment time by product/site.

MC2-01 cream will be compared with Clobex® lotion, Betamethasone Dipropionate (Augmented) cream, Triamcinolone Acetonide cream, Locoid® cream, DesOwen® cream and MC2-01 cream vehicle in terms of visual score of skin blanching 2 hours after a 16 hours application, using an ANOVA with subjects and treatments as factors.

Some minor changes in the protocol statistical methods have been decided and reported in the SAP to improve the data analysis of the primary criterion.

The protocol planned that In case of a significant treatment effect, estimates of treatment effect and 95% confidence interval of differences between reference products and MC2-01 cream will be calculated from the model without correction for multiplicity in the primary analysis and that correction for multiplicity using Dunnett's test will be used as secondary analysis. In case of significant deviation to the normal assumption, a non-parametric approach with Kruskall-Wallis test for the overall product effect and Wilcoxon's Sign Rank Test for the pairwise comparisons will be used

The present Statistical Analysis Plan states that In case of a significant treatment effect, the comparisons between reference products and MC2-01 cream will be done from the model with correction for multiplicity using Dunnett's test directly in the primary analysis. For each fitted model, residual plots will be used to check the model assumptions. If there is an obvious deviation to these assumptions, the analysis will be done on the rank-transformed data.

The data will be also presented graphically by treatment using boxplot of visual assessment of skin blanching.

Statistical Analysis Plan MC2-01-C4 / CPCAD CPC-3530 Version 2.0 dated 05-Dec-2018 Page 14/16

The results will be presented as follows:

	MC2-01 cream (n=XX)	Clobex® lotion (n=XX)	Betamethasone Dipropionate (Augmented) cream (n=XX)	Triamcinolone Acetonide cream (n=XX)	Locoid® cream (n=XX)	Desowen® cream (n=XX)	MC2-01 cream vehicle (n=XX)
N Mean±SD Median (Min,Max)							
p-value a (treatment comparison versus MC2-01 cream)	-						

a: method used for multiple comparisons

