#### Short Title :

A vasoconstriction test trial with a MC2-01 cream (ranking trial).

Sponsor Trial Number:	MC2-01-C4
Clinical Trial Phase:	Phase 1
Investigator:	[name] [name]
Co-Investigator:	[name] [name]
Clinical Trial Population:	Healthy subjects, males and females, aged 18 to 50 years old.
Clinical Trial Objectives:	The objective of this trial is to compare the vasoconstriction potential (skin blanching effect) of MC2-01 cream with Clobex 0.05% (clobetasol propionate) lotion, Betamethasone Dipropionate (Augmented) 0.05% (betamethasone dipropionate) cream, Triamcinolone Acetonide 0.1% (triamcinolone acetonide) cream, Locoid ® 0.1% (hydrocortisone butyrate) cream, Desowen ® 0.05% (desonide) cream and MC2-01 vehicle using the human skin blanching test (McKenzie-Stoughton's test).
Background:	Topically applied corticosteroids elicit a pharmacologic activity (blanching) viewed by many as being "vasoconstrictive" in nature. The skin blanching effect was first described by Mc Kenzie and Stoughton (1) in 1962. This pharmacodynamic response has been correlated with the clinical efficacy of the product in psoriasis (2) and used for years to determine the clinical potency of topical corticosteroid formulations and to classify them within the US topical steroid potency classification.
	MC2 Therapeutics has developed an innovative dermal pharmaceutical formulation containing calcipotriol (CAL) 0.005 % w/w (50 $\mu$ g/g) and betamethasone dipropionate (BDP) 0.064 % w/w (0.5 mg/g as betamethasone), MC2-01 cream to ease local application of pharmaceuticals and to significantly enhance local cutaneous penetration of the active ingredients.
	Currently marketed products are restricted to non-oil-based formulations as calcipotriol and betamethasone are characterized by having a potential incompatibility to exist together in an environment, since calcipotriol requires basic conditions to maintain stability while betamethasone requires acidic conditions.

CPCAD Nice	C P C A D
Clinical Trial Protocol MC2-01-C4	Final Approved Version 20/08/2018
	MC2-01 cream has been formulated using the PAD ™ Technology allowing sufficient protection of the drug substances from degradation during storage.
Clinical Hypothesis:	The blanching effect of the MC2-01 cream is expected to be lower than Clobex, not significantly different from Betamethasone Dipropionate (Augmented) cream and higher than the other references.

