## 10.1.3 Method of treatment assignment

Prior to the start of the trial, a randomization list will be generated by a statistician from CPCAD and will be transmitted to the person in charge of the products application.

Clinical Trial Protocol MC2-01-C4

The list will indicate the assignment of the seven products to the seven different test sites (1-7) of each Subject, according to a Latin squares design. The order of applications will be 1 to 7 for all Subjects.

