#### 13.2.1 Primary pharmacodynamic criterion

The analysed variable will be the mean between the two readers at each evaluation time.

The results will be expressed by the mean values obtained at each assessment time by product/site.

MC2-01 cream will be compared with Clobex lotion, Betamethasone Dipropionate (Augmented) cream, Triamcinolone Acetonide cream, Locoid® cream, DesOwen cream and MC2-01 cream vehicle in terms of visual score of skin blanching 2 hours after a 16 hours application, using an ANOVA with subjects and treatments as factors. The mean of visual assessments obtained at the same time points from 2 independent trained readers will be used. In case of a significant treatment effect, estimates of treatment effect and 95% confidence interval of differences between reference products and MC2-01 cream will be calculated from the model without correction for multiplicity in the primary analysis. Correction for multiplicity using Dunnett's test will be used as secondary analysis. In case of significant deviation to the normal assumption, a non-parametric approach with Kruskall-Wallis test for the overall product effect and Wilcoxon's Sign Rank Test for the pairwise comparisons will be used.

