### 13.5 Number of subjects calculation

The null hypothesis for each pairwise comparison will be no difference in the human skin blanching test :

H0: ∆ = 0,

where  $\Delta$  is the mean difference in visual score between test sites with the compared treatments. The standard assumptions of normality and independence will be used.

According to previous vasoconstriction trial performed by CPCAD, a maximal standard deviation for the difference of 0.65 is assumed.

Using a paired t-test, a two-sided significance level of 5%, with 30 complete subjects, the probability of detecting a difference of 0.5 units assuming a standard deviation for the difference of 0.65 is 98%.

MC2-01 cream will be compared to the five steroid-containing reference products giving at least 92% (0.98) power to obtain 5 significant differences if the true difference with each reference product is at least 0.5 int. MC2-01 cream will also be compared to the matching MC2-01 cream vehicle, but that will have negligible impact on the overall power assuming a difference of at least 1 point between both products.

A total of 36 subjects will be randomized in this trial in order to obtain at least 30 completed evaluable subjects.

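### The primary ANOVA omits test site, although products are allocated to sites 1-7 by Latin squares; adding it costs almost nothing and recovers precision if site or application order matters

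*SAP*

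**What the plan says.** Protocol 10.1.3 describes a randomisation list giving the "assignment of the seven products to the seven different test sites (1-7) of each Subject, according to a Latin squares design". The same section adds: "The order of applications will be 1 to 7 for all Subjects". Protocol 10.1.6 places sites 1 to 4 on one forearm and 5 to 7 on the other, running from elbow to wrist.

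The primary analysis does not use this structure. Protocol 13.2.1 compares the products on "visual score of skin blanching 2 hours after a 16 hours application, using an ANOVA with subjects and treatments as factors". SAP 5.2.1 keeps the same two-factor model, "using an ANOVA with subjects and treatments as factors". The SAP does revise the multiplicity method (Dunnett now in the primary analysis) and the fallback (rank-transformed data), but it adds no site, arm or order term. Neither document says why site is left out. The data needed are collected: per SAP 4.1, "Two visual score values (one per trained evaluator) will be recorded for each test site".

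The sample-size section (protocol 13.5) states that, with 30 complete subjects and a paired t-test, "the probability of detecting a difference of 0.5 units assuming a standard deviation for the difference of 0.65 is 98" per cent. The synopsis expects MC2-01 cream to blanch less than the clobetasol lotion, to be "not significantly different from Betamethasone Dipropionate (Augmented) cream and higher than the other references".

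**The concern.** A Latin square blocks on two factors, here subject and site. The plan fits only the first. Because application order is the site number in everyone, one seven-level factor carries both forearm position and order.

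If blanching varies with that factor, the near-balanced allocation keeps the variation mostly out of the treatment differences, so the estimates are essentially unbiased either way. The variation still enters the residual mean square when site is not fitted. The reported standard errors then exceed the true sampling error of the differences, and the tests are conservative.

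Two things are at stake. Separation from neighbouring potency classes is weaker than the design allows for differences below 0.5 units. And for the comparison with augmented betamethasone dipropionate, where the hoped-for result is non-significance, a larger standard error is not conservative: it makes that result easier to reach than it would be with site fitted.

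**Working it through.** **Inputs from the documents.** SD of a paired difference 0.65, planned difference 0.5, 36 randomised and 30 complete (protocol 13.5); two-sided 5% (SAP 5.4); Dunnett for six comparisons with MC2-01 cream (SAP 5.2.1); a subject with a missing primary score is dropped whole (SAP 5.4.1).

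**Assumption.** The share s of within-subject variance due to site is not in the documents. The range 0, 10, 20 and 30% is shown.

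**The plan's own figure.** Noncentrality = 0.5 / (0.65/√30) = 0.5 / 0.1187 = 4.21 on 29 df. Exact paired t power is 98.3%, and its fifth power is 91.6%. The stated 98% and 92% reproduce.

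**Degrees of freedom.** With 30 subjects: 7 × 30 − 30 − 6 = 174 without site and 174 − 6 = 168 with it. The Dunnett cut-off moves from 2.591 to 2.593.

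**Standard errors.** Total within-subject variance is 0.65²/2 = 0.211, split into s (site) and 1 − s (error), so that the SD of a difference stays at 0.65.
- Without site: SE = 0.65/√30 = 0.119, whatever s is.
- With site: SE = 0.1187 × √(1 − s).
- Ratio: 1/√(1 − s).
- Dunnett half-width: cut-off × SE, for example 2.591 × 0.1187 = 0.307.

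**Power.** Simulated with randomised 7 × 7 squares cut at 36, a random 30 kept, and a linear gradient by position on each arm. There were 4,000 runs per cell (6,000 for the 0.3-unit row), so the Monte Carlo standard error near 80% is √(0.8 × 0.2/4000) = 0.6 points.

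| Site share s | 0% | 10% | 20% | 30% |
|---|---|---|---|---|
| Highest minus lowest site (units) | 0 | 0.39 | 0.55 | 0.68 |
| SE with site (0.119 without) | 0.119 | 0.113 | 0.106 | 0.099 |
| SE ratio, without/with | 1.00 | 1.05 | 1.12 | 1.20 |
| Dunnett half-width with site (0.307 without) | 0.308 | 0.292 | 0.275 | 0.257 |
| Dunnett power at 0.4, without / with | 77 / 77% | 80 / 83% | 81 / 88% | 80 / 92% |
| Dunnett power at 0.5, without / with | 94 / 94% | 95 / 96% | 96 / 98% | 96 / 99% |
| Non-significant at true 0.3, without / with | 54 / 54% | 52 / 47% | 53 / 42% | 54 / 34% |

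Unadjusted power at 0.5 units without site is about 99% throughout. The per-comparison error rate at the Dunnett cut-off is 0.9/0.6/0.6/0.2% without site and about 1% with it, which is the conservatism described above. Replacing the gradient by a trend over sites 1 to 7 (application order) gives 78 vs 82%, 79 vs 87% and 81 vs 92% at 0.4 units for s = 10, 20 and 30%.

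**Loss of balance.** 36 is not a multiple of 7. Relative to complete squares, fitting site raises the SE by 0.04% with all 36 subjects, and by 0.3% on average (at most about 0.8%) with a random 30 of 36.

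**The case against.** The strongest reply is that the defect is hypothetical. No site effect is reported, and every non-zero figure rests on an assumed share. The 12% and 20% penalties need site ranges of 0.55 and 0.68 units, larger than the 0.5-unit difference the trial is sized on; at a 5% share the penalty is about 3%. The protocol also limits positional variation through margins from elbow and wrist, avoidance of veins and hair, exclusion of subjects whose arms differ visibly in colour, and a constant room temperature. This stands as a limit on how large the effect may be.

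The gradient above is also the same for every product, whereas a site that barely blanches has little response to vary. With the site effect proportional to response (assumed product means 2.5, 2, 2, 1.5, 1, 0.5 and 0), the excess in SE falls from 5/12/20% to about 2/5/9%, and Dunnett power at 0.5 units is 97 vs 97%, 97 vs 98% and 98 vs 99%. With an additive effect clipped at zero the excess is 4/10/17%. So the table is towards the upper end for a given share, though a gain remains. Site number is moreover only a proxy for position, since the arm carrying sites 1 to 4 is not fixed and the layout may be staggered.

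The SD of 0.65 is described as maximal and applies to the raw difference, so it probably already includes site variance; the sample size then allows for this noise. That is right, and it is why no breach of the planned power is claimed. It also follows that the chance of non-significance at 0.3 units stays at 52 to 54% without site: the plan forgoes an improvement rather than making matters worse than its own SD implies.

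None of this gives a reason to leave out the factor the trial randomises by.

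**Conclusion.** The point holds as a forgone gain in precision. The allocation blocks on site, the model does not, and no reason is given. If site or order carries 10 to 30% of within-subject variance, standard errors are 5 to 20% larger than needed under a common additive effect, and about 2 to 9% larger if the effect scales with response. With no site effect nothing material changes.

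Planned power is not breached, the estimates are essentially unbiased and false positives are not inflated. The practical effect is on differences below 0.5 units and on the betamethasone dipropionate comparison: at a 20% share, an assumed true difference of 0.3 units is missed 53% of the time without site and 42% with it. A site term lessens that but does not cure the separate problem of inferring similarity from non-significance. The true share cannot be fixed from the documents, and no claim is made about left versus right arm. The change is worth making because it is nearly free, not because the plan fails without it.

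**What to change.** In SAP 5.2.1, specify an ANOVA with subject, treatment and test site (1 to 7) as factors. Take the Dunnett comparisons, any confidence intervals and the rank-transformed fallback from that model. Otherwise, state in one sentence why site is left out. Either way this should be settled before the randomisation code is broken, since adding the term afterwards would be post hoc.

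The cost is one factor and 6 of 174 residual degrees of freedom. With no site effect, power changes by less than 1 point. Site number is already in the randomisation list and scores are recorded by site, so no new data, visits or subjects are needed. The site term also handles the slight imbalance from 36 not being a multiple of 7 and from dropouts, so the number randomised can stay as it is.
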